1 PROTOCOL SUMMARY

1.1 SYNOPSIS

Title:	A Phase II Study of Fostamatinib to Treat Post-transplant Immune-mediated Cytopenias
Study Description:	This open label phase II trial is designed to evaluate the efficacy of fostamatinib in the treatment of post-transplant cytopenias as assessed by hematologic improvement in anemia and/or thrombocytopenia following a 12-week treatment course. Patients who respond to the 12-week treatment course on this single arm study are eligible and have the option to enroll on the extended access trial.
Objectives:	
The primary objective is to assess efficacy of fostamatinib for stable hematologic recovery during post-hematopoietic stem cell transplant immune mediated anemia and/or thrombocytopenia.
 
The secondary objective is to assess efficacy of fostamatinib for clinically-relevant outcomes in post-hematopoietic stem cell transplant patients.
 
The exploratory objective is to evaluate changes in serologic markers that may be associated with cytopenias while on treatment to identify key elements for fostamatinib response.

Endpoints:	
Primary endpoints:
 
The proportion of subjects with hematologic recovery that is stable, defined as improvement documented in 2 consecutive available readings at least 2 weeks apart, without recent blood product transfusion support in the past 7 days.
 
Hematologic recovery is defined as:
 
 • Hemoglobin ≥ 10 g/dL (or at least ≥ 2 g/dL above baseline) in subjects enrolled with posttransplant anemia. In subjects with symptomatic anemia, a hemoglobin increase of at least ≥ 2 g/dL above baseline is required 
OR
 
 • Platelets $\geq 50 \times 10^9/L$ (or at least $\geq 20 \times 10^9/L$ above baseline) in subjects enrolled with posttransplant thrombocytopenia 
OR
 
 • Both of the above criteria in subjects with posttransplant Evans syndrome 
Secondary endpoints:
 
 1. Proportion of subjects who achieve objective hematologic recovery within the 12-week treatment course defined as:

Abbreviated Title: Fostamatinib for post-transplant cytopenias

Version Date: 11/28/2023

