	
 • Hemoglobin ≥ 9 g/dL (or at least ≥ 1 g/dL above baseline) in subjects enrolled with anemia or at least ≥ 1 g/dL above baseline in subjects with symptomatic anemia 
OR
 
 • Platelets $\geq 30 \times 10^9/L$ (or at least $\geq 10 \times 10^9/L$ above baseline) in subjects enrolled with thrombocytopenia 
OR
 
 • Either of the above criteria in subjects with Evans syndrome 
 2. Average weekly requirement of transfused blood component or growth factor requirement (total units of PRBC or Platelets/week, total dose of growth factor/week) by week 12, compared to the week prior to the start of the study drug. 3. Change in corticosteroid dose over time, measured by median daily weight-based prednisone-equivalent corticosteroid dose in a week, from week 1 to week 12 4. Change in other immunosuppressant dose over time, measured by median daily dose of the immunosuppressant in a week, from week 1 to week 12 5. Number of patients who achieved $\geq 50\%$ steroid dose reduction by week 12 compared to week 1 6. Incidence and severity of cGVHD according to 2014 NIH Consensus Criteria, at baseline before the initiation of treatment, and at week 12 
Exploratory endpoints:
 
 1. Absolute percentage change in B cell chimerism pre-treatment, vs weeks 4 and 12. 2. cPRA change in the preformed HLA antibodies before and after treatment in subjects with thrombocytopenia or Evans syndrome 3. Percent MFI change of preformed HLA antibodies before and after treatment. This applies for antibodies with an MFI $>1,000$. 4. Anti-RBC alloantibody titer change in patients with hemolytic anemia before and after treatment 5. Assessment of serial cytokines pre-treatment and weeks 4 and 12. Cytokines include CRP, IL-1, IL-2, IL-6, IFNγ, TNFα, EPO and TPO 6. Immunoglobulin level changes pre-treatment, and weeks 4 and 12. 7. Absolute reticulocyte count, lactate dehydrogenase, haptoglobin changes pre-treatment, and at each biweekly study visit, in patients with anemia or Evans syndrome 8. Change in the weekly rate and severity of bleeding according to the total score of the ITP-Bleeding Scale (IBLS), from week -1 (one week before the start of the study drug) to week 12, in subjects with thrombocytopenia or Evans syndrome

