5.1 INCLUSION CRITERIA

- Ages 18-75 years inclusive
- Ability to comprehend the investigational nature of the study and provide informed consent
- Female patients of reproductive potential agree to avoid pregnancy through abstinence or the use of two forms of highly effective birth control during and for 1 month after the last study treatment and agree not to donate eggs during this time
- Male patients of reproductive potential agree to avoid pregnancy of a partner through abstinence or the use of two forms of highly effective birth control during and for 1 month after the last study treatment and agree not to donate sperm during this time.
- Diagnosis of an immune mediated cytopenia (anemia and/or thrombocytopenia)[‡] in a patient that either:
 - Failed or relapsed after at least one line of therapy including steroids, IVIG, TPO mimetics, rituximab, azathioprine, cyclophosphamide, cyclosporine, tacrolimus, danazol, vincristine, ESA or splenectomy
 - Or remains transfusion dependent (≥ 1 transfusion(s)/2 weeks)
 - Or is steroid dependent*
- Subjects are ≥ 60 days post-allogeneic transplant with:
 - Thrombocytopenia, defined as average platelets count $< 30 \times 10^9/L$ for 3 consecutive available readings at least 2 weeks apart, after other cell lines have engrafted, with no counts $> 40 \times 10^9/L$ unless from rescue transfusions. Subjects failed at least one line of therapy outlined above with a clinical diagnosis of immune mediated thrombocytopenia.

- Anemia, transfusion dependent, or defined as hemoglobin ≤ 9 g/dL for 3 consecutive available readings at least 2 weeks apart, after other cell lines have engrafted OR if hemoglobin 9-10 g/dL, subject must have symptomatic anemia or ongoing treatment for immune hemolytic anemia that have failed at least one line of therapy outlined above. Symptomatic anemia is defined as anemia with fatigue, weakness, shortness of breath, palpitations/fast heartbeat, lightheadedness, and/or chest pain, and these symptoms are attributed to anemia. Laboratory evaluation are recommended but not required for the diagnosis, such as a positive DAT, low haptoglobin $<$ lower limit of normal (LLN), indirect bilirubin $>$ upper limit of normal (ULN), or lactate dehydrogenase (LDH) $>$ ULN.
- Subjects must test negative for HIV, HBV, and HCV by standard serologic tests within the previous six months

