- Subjects on other standard of care therapeutic regimens for GVHD or cytopenias should be on a stable dose of medication (no change $\geq 25\%$) for at least 15 days prior to enrollment.
- Patients with a history of hypertension should be maintained on a stable antihypertensive regimen and with controlled blood pressure (Systolic blood pressure < 140 mmHg and diastolic blood pressure < 90 mmHg) for at least one week prior to enrollment.
- Peripheral blood or bone marrow T-cell chimerism $\geq 50\%$ donor cells
- [‡] Immune mediated anemia in subjects with auto or alloantibodies identified due to ABO or non-ABO mismatch transplant, or thrombocytopenia due to identified HLA/HPA antibody. Other causes of immune mediated cytopenias include clinically diagnosed (with or without serologic confirmation) idiopathic thrombocytopenic purpura or autoimmune hemolytic anemia. Subjects with cytopenias attributable to GVHD will be included. Subjects with idiopathic immune mediated cytopenias can also be included. Subjects with evidence for graft rejection per the investigator's opinion ARE NOT eligible for treatment.

* Steroid dependence is defined as inability to tolerate a corticosteroid taper after demonstrating a response to an initial corticosteroid dose (typically 1-2 mg/kg/day). Patients will meet our definition of steroid dependence if their cytopenias relapse or progress before achieving a 50% decrease in the initial corticosteroid dose and/or are unable to have their steroid dose tapered to a dose of less than 20 mg/day of prednisone.

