5.2 EXCLUSION CRITERIA

- Severe psychiatric illness or mental deficiency sufficient to make making informed consent impossible
- Positive pregnancy test for women of childbearing age within 1 week or being actively lactating
- Immune mediated cytopenia responsive to the standard of care treatment
- Immune mediated cytopenia due to other autoimmune causes, such as systemic lupus erythrocytosis, chronic lymphocytic leukemia
- Patients who have previously received or currently take fostamatinib post-allogeneic transplant
- Non-immune mediated cytopenias. Etiologies including, but not limited to, cytopenias due to HIV infection, lymphoproliferative disorders, myelodysplasia/acute leukemia, drug-induced thrombocytopenia, thrombotic microangiopathies, acute bleeding, consumptive coagulopathy, fever, infections leading to cytopenia, medications induced cytopenias, thrombotic microangiopathies (disseminated intravascular coagulation), splenomegaly or hemophagocytic lymphohistiophagocytosis, relapse of primary disease.
- Patients with neutropenia, defined as absolute neutrophil count $\leq 1.0 \times 10^9/L$, will be excluded
- Uncontrolled hypertension (systolic blood pressure ≥ 140 mmHg or diastolic blood pressure ≥ 90 mmHg)

Abbreviated Title: Fostamatinib for post-transplant cytopenias

Version Date: 11/28/2023

- ALT or AST ≥ 3 times the upper limit of normal, or direct bilirubin ≥ 2 times the upper limit of normal
- Patients who have a history of medical disorders, that in the investigator's opinion, could affect the conduct of the study or the absorption, metabolism or excretion of the study drug are excluded.
- Patients with lymphoma/chronic lymphocytic leukemia, hepatitis, or HIV associated with ITP/wAIHA
- Patients with evidence of graft rejection (based on clinical suspicion supported by BM biopsy data and/or chimerism studies and/or MLR)
- Subjects recently treated (within 30 days) with cytokine-targeting biologics (anti-TNF, IL6) or B-cell or plasma-cell depleting antibody.
- Other cancers except that for which the transplant was done < 2 years before study entry, except non-melanoma skin cancer or carcinoma in situ of the uterine cervix or breast

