8.2.2 Biospecimen Evaluations

Research bloods will be sent to the NIH for processing in either the clinical laboratory or in a NHLBI research lab.

The amount of blood that may be drawn from adult patients (i.e., those persons 18 years of age or older) for research purposes shall not exceed 300 mL over any eight-week period.

Please refer to laboratory manual for further information about processing and shipment.

Table of samples to be collected*				
Test/assay	Volume blood (approx.)	Type of tube	Frequency	Location of specimen analysis
Routine* 
 • CBC • Absolute reticulocyte count • BMP • Hepatic pane • Lactate dehydrogenase • haptoglobin 	3 mL 4 mL	EDTA tube Lithium Heparin tube (light green)	Baseline (prior to treatment) and then biweekly on follow up visits	NIH clinical lab or Clinical Lab At participating sites
Research* 
 • STR Chimerism, CD19 	6 ml	EDTA tube	Baseline, then W4,8,12	NHLBI Research Lab ([name]), NIH Clinical Lab (Molecular Hematology, 2C324)
Research* 
 • Type and screen 	6 mL	EDTA tube	Baseline, then W4, 8, 12	NIH Clinical Lab or, Clinical Lab At participating sites**

Abbreviated Title: Fostamatinib for post-transplant cytopenias

Version Date: 11/28/2023

Table of samples to be collected*				
Test/assay	Volume blood (approx.)	Type of tube	Frequency	Location of specimen analysis
Research* • Immunoglobulins, quantitative (IgA, IgG, IgM)	3.5 mL	Lithium Heparin tube (light green)	Baseline, then W4, 8, 12	NIH Clinical Lab Or, Clinical Lab At participating sites***
Research* • HLA antibodies (Class 1 A, B, C and Class 2 DRB1, DQB1) • MFI	10 mL	EDTA tube	Baseline, then W4, 8, 12	NIH Clinical Lab
Research* • CRP	4 mL	Lithium Heparin tube (light green)	Baseline, then W4, 8, 12	NIH Clinical Lab or Clinical Lab At participating sites
Research* • Erythropoietin	3.5 mL	Red top tube (SST3.5)	Baseline, then W4, 8, 12	NIH Clinical Lab
Research* • IL-6	6 mL	EDTA (lavender)	Baseline, then W4, 8, 12	NHLBI Research Lab ([name])
Research* • Expanded cytokine panel • Thrombopoietin	16 mL	Red top tube (serum)	Baseline, then W4, 8, 12	NHLBI Research Lab ([name])
Research* • Lymphocyte subsets • PBMC	20 mL	Sodium Heparin (green top)	Baseline, then W4, 8, 12	NHLBI Research Lab ([name])

* Residual bloods from clinical care can be transferred to the NHLBI research lab for storage

Abbreviated Title: Fostamatinib for post-transplant cytopenias

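### Exploratory endpoint 6 analyses raw IgG change without regard to IVIG, so in subjects given IVIG near a research draw the change partly measures infused product

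*Combined protocol and SAP*

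**What the plan says.** The exploratory objective in the Synopsis is to "evaluate changes in serologic markers that may be associated with cytopenias while on treatment to identify key elements for fostamatinib response". Endpoint 6 serves it with "Immunoglobulin level changes pre-treatment, and weeks 4 and 12". The sample table in Section 8.2.2 lists quantitative IgA, IgG and IgM at baseline and weeks 4, 8 and 12. Endpoint 5 covers serial cytokines at the same pre-treatment, week 4 and week 12 points: "Cytokines include CRP, IL-1, IL-2, IL-6, IFNγ, TNFα, EPO and TPO".

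Four places bear on administered product:

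- Section 5.1 names IVIG and ESA among the qualifying therapies: "Failed or relapsed after at least one line of therapy including steroids, IVIG, TPO mimetics, rituximab, azathioprine, cyclophosphamide, cyclosporine, tacrolimus, danazol, vincristine, ESA or splenectomy".
- Section 5.1 also lets background treatment continue: "Subjects on other standard of care therapeutic regimens for GVHD or cytopenias should be on a stable dose of medication", with no change of 25% or more for at least 15 days before enrollment.
- The recent-treatment exclusion in Section 5.2 reads "Subjects recently treated (within 30 days) with cytokine-targeting biologics (anti-TNF, IL6) or B-cell or plasma-cell depleting antibody". Neither IVIG nor ESA is in it.
- Section 6.5 limits the medications reported in the CRF to prescription drugs used for post-transplant cytopenias.

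Section 9.3.3 plans descriptive summaries of the exploratory endpoints, with paired or regression analysis where appropriate. It names no covariate, exclusion or sampling window. Section 3.1 confirms that there is no control arm.

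**The concern.** A quantitative IgG assay reports total IgG. If a subject had IVIG before the baseline draw and none afterwards, total IgG falls as the infused protein clears, whatever fostamatinib does. If IVIG is started or increased on study, total IgG rises. The plan computes the same raw change for these subjects as for unexposed ones and pools them.

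What is at stake is the reading of one mechanistic marker. IgG change is meant to help explain response to a drug thought to act partly through B cells. A subject whose counts improve may also be one whose supportive treatment is withdrawn, so a fall in IgG could line up with response for a reason unrelated to the drug.

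The protocol already guards against administered product elsewhere. Baseline hemoglobin and platelets must be taken at least 72 hours after the last transfusion (Section 4, footnote), and a response reading requires no transfusion in the past 7 days. Endpoint 6 has no comparable guard.

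**Working it through.** The plan states no figure for this point, so there is nothing to reproduce. The check has two parts.

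**1. Does any rule in the text remove the overlap?**

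- *Entry:* the 15-day stability rule permits ongoing IVIG and does not remove carry-over from a dose given before that window. The 30-day exclusion does not cover IVIG.
- *On study:* no section fixes, prohibits or times IVIG relative to the research draws.
- *Measurement:* the assay listed is total immunoglobulin by class, with nothing that separates infused from own IgG.
- *Data:* concomitant medications are reviewed at each visit (Schedule of Activities, note a), and cytopenia prescriptions go in the CRF. IVIG given for another reason falls outside Section 6.5 and could go unrecorded.
- *Analysis:* Section 9.3.3 allows regression but does not tie any exposure to any marker.

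No rule removes it.

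**2. How large could it be in one exposed subject?**

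Assumptions, none of them in the documents: a single IVIG dose of 1 g/kg, distribution volume 0.1 L/kg, half-life 25 days, own IgG constant, no further IVIG, no drug effect.

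Initial infused IgG = dose / volume = 1 g/kg ÷ 0.1 L/kg = 10 g/L = 1,000 mg/dL.

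Infused IgG remaining t days after the dose = 1,000 × 0.5^(t/25). Weeks 4 and 12 are 28 and 84 days after baseline.

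| Dose before baseline | Baseline | Week 4 | Week 12 | Fall by week 12 |
|---|---|---|---|---|
| 7 days | t = 7: 824 | t = 35: 379 | t = 91: 80 | 824 − 80 ≈ 740 mg/dL |
| 15 days | t = 15: 660 | t = 43: 304 | t = 99: 64 | 660 − 64 ≈ 595 mg/dL |

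The 15-day row is the easier one to square with the stability rule, since a new infusion a week before baseline would arguably breach it.

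Range over doses of 0.4 to 2 g/kg and half-lives of 21 to 30 days, with volume held at 0.1 L/kg:

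- Dose 7 days before baseline: about 290 to 1,490 mg/dL.
- Dose 15 days before baseline: about 230 (400 × 0.571) to 1,210 mg/dL (2,000 × 0.606).

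**What this does to a group summary.** The number exposed is unknown, so this too is only illustrative. Suppose infused IgG is 20% to 50% of baseline total IgG, the half-life is 3 weeks, and 4 of 20 subjects stop IVIG at baseline. The mean percent change at week 12 is then −(4/20) × share × (1 − 0.5^(12/3)) = −0.2 × share × 0.9375. That is −3.8% for a 20% share and −9.4% for a 50% share, with no drug effect.

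**The case against.** The case against giving this much weight is fair in several respects.

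- These are exploratory, descriptive markers. Nothing in the primary test, its error rates or the stopping rules depends on them. This stands, and it limits the importance of the point.
- A listed prior therapy is not a current one. IVIG is one of twelve therapies a subject may have failed, and no section gives an expected number receiving it at baseline. This stands, so the size for the trial cannot be stated.
- A single decaying dose does not describe a stable repeating regimen. This also stands. With regular IVIG throughout, the infused share may change little, and the distortion then depends on where each draw falls in the dosing cycle.
- Much of the data is already collected: cytopenia prescriptions are in the CRF, and growth factor dose per week is needed for secondary endpoint 2. True, but nothing links these records to the marker analysis, and IVIG for other indications is not clearly covered.

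A reader might infer more than the documents support, in three ways.

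- *That endpoints 5 and 6 cannot inform on response at all.* Only IgG among three immunoglobulin classes, and EPO among eight listed analytes, are open to this problem.
- *That the study hypothesis predicts falling IVIG use, so IgG must drift down.* The hypothesis statements (Sections 2.2 and 2.3.3) name transfusion, growth factors and immunosuppressive therapies, not IVIG. A fall in IVIG use is at most implied, and starting IVIG pushes IgG up.
- *That EPO is distorted to the same degree.* Injected ESA could in principle be read by an erythropoietin assay, and growth factor use is expected to fall. But the documents name neither the agent nor the assay, so no size can be given.

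**Conclusion.** The point holds for IgG. Followed as written, the plan yields IgG changes that combine infused and own protein in any subject given IVIG near a research draw, in either direction and with no control group for comparison. In one such subject the artefact could be several hundred mg/dL: about 595 to 740 by week 12 for a 1 g/kg dose 15 to 7 days before baseline. That figure rests on the assumed dose, volume and half-life, and on IVIG not being repeated. The effect on the trial's summary depends on the number exposed, which is not given.

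IgA and IgM are not affected, on the assumption that the infused product is essentially IgG. For EPO the same caution applies in principle, at unknown size. The other cytokines, the primary endpoint and the stopping rules are untouched. This is a cheap and worthwhile improvement to one exploratory analysis, not a threat to the trial's conclusions.

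**What to change.** 1. In the CRF, record the date and dose of any IVIG, whatever the indication, and of any ESA, so that each can be placed relative to each research draw. Section 6.5 should be worded so that IVIG given for reasons other than cytopenia is captured.
2. In Section 9.3.3, make IgA and IgM change, already measured, the main immunoglobulin readout.
3. Report IgG change separately for subjects with and without IVIG in a pre-set interval before either of the two samples compared. Flag exposed values rather than discarding them. Excluding everything within, say, three half-lives would mean about 63 to 90 days at half-lives of 21 to 30 days, and would remove the baseline value, and with it the paired change, for any recently treated subject in a 20-subject trial.
4. Flag EPO values drawn on ESA in the same way, and state that the size of that effect is unknown until the agent and assay are specified.

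The cost is one or two CRF fields, a few sentences in the analysis section, and fewer subjects in the unexposed IgG and EPO summaries. No visit, blood draw or treatment rule changes.

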1.2 SCHEMA

All subjects will receive fostamatinib 100 mg BID for 4 weeks. On the 4-week evaluation,

- a) if the cytopenia/s improves (hemoglobin ≥10 g/dL and/or platelets ≥ 50 x 10⁹/L), patients will continue the same dose for a total of 12 weeks; b) if refractory cytopenias persist (hemoglobin < 10 g/dL, platelets < 50 x 10⁹/L), pts will increase dose to 150 mg BID.

* Subjects with persistent (≥2 readings, 2 weeks apart) loss of hematologic response after week 5 can increase dose to 150mg BID until end of the study on week 12.

*Temporary drug interruption: Patient to receive total of 12 weeks of fostamatinib despite drug interruptions. If patient have drug interruptions, patient will be maintained in protocol until finishing the total 12 weeks of the treatment.

Abbreviated Title: Fostamatinib for post-transplant cytopenias
Version Date: 11/28/2023

1.3 SCHEDULE OF ACTIVITIES (SOA)

Study Week ^k	-1	0	2 ^d	4 ^d	6 ^d	8 ^d	10 ^d	12 ^d	14 ^{e,f} (end of study safety visit)
Informed Consent	X ^b	X ^b							
Inclusion/exclusion	X ^b	X ^b							
Pregnancy Test	X ^b	X ^b		X		X		X	
HIV, HBV, HCV testing	X ^{b,j}	X ^{b,j}							
Medical History	X ^b	X ^b							
Medical assessment ^a	X	X	X	X	X	X	X	X	X
Physical Exam	X ^b	X ^b							
Follow up and labs ^{c,d} : CBC, BMP, LFTs, LDH, absolute reticulocyte count, haptoglobin, stool occult blood, urinalysis	X ^b	X ^b	X	X	X	X	X	X	X
Study drug (fostamatinib) administration ^g		X	X	X	X	X	X		
B-cell chimerism and Cytokines ^h		X ^b		X		X		X	
IBLS [1] ⁱ	X ^b	X ^b	X	X	X	X	X	X	
cPRA, MFI, immunoglobulin level, RBC antibody		X		X		X		X	

- a) Vital signs, transfusion support evaluation, concomitant medication review and steroids taper assessment
- b) Can be done within 7 days before or at time of enrollment
- c) Follow up visits will be completed as outpatient in-person visits at the NIH Clinical Center, or via telehealth/telephone if patients are unable to travel for any reason (except for weeks 4 and 12 where patients are required to return to the NIH Clinical Center). Labs can be completed locally, and results will be provided to the research team.
- d) Can be performed +/- 4 days from scheduled visit.
- e) Outpatient visit can be +/- 3 days from scheduled visit.
- f) Patients who rolled over to 000760-H will not need to return for week 14 visit, they will transition all study follow up to 000760-H. The patients who do not roll over will complete their week 14 safety visit on 000758-H.

Abbreviated Title: Fostamatinib for post-transplant cytopenias

Version Date: 11/28/2023

- g) Study drug will be mailed from Rigel or the clinical center pharmacy and be distributed to the research subjects from the pharmacy directly to the research subjects. The pill count will be reviewed every 2 weeks at the medical assessment visit.
- h) Including CRP, IL-1, IL-2, IL-6, IFN γ , TNF α , EPO and TPO
- i) See Appendix B
- j) Within 6 months
- k) Temporary drug interruption. Patient to receive total of 12 weeks of fostamatinib despite drug interruptions. If patient have drug interruptions, patient will be maintained in protocol until finishing the total 12 weeks of the treatment. Treatment may be delayed for a maximum of 14 days after holding the treatment for toxicities that develop and do not resolve as defined at 6.1.2.3 (neutropenia, LFT elevation, and diarrhea). The timing of subsequent lab and the study week are then adjusted to the study week that was stopped.

